A growing body of literature suggests that FPP may have beneficial effects on age-related proinflammatory disease conditions (Marotta et al., 2007). However, to our knowledge, no study has tested the effects of FPP on cerebral energy metabolism, neuroinflammation and cognitive function in humans under controlled conditions. Thus, we aim to conduct a double-blind, randomized, placebo-controlled pilot study on FPP in older adults. If FPP is found to have a beneficial impact on cerebral energy metabolism, neuroinflammation and cognitive function in our study population (adults aged 65-100), then this product may be a potential treatment option to combat cognitive aging and age-related decline in brain function. The specific aims and hypotheses of the proposed pilot study are the following:

Aim #1. To determine the effect of FPP on cerebral energy metabolism.

Hypothesis: FPP will increase cerebral energy metabolism markers on alpha ATP, beta ATP, gamma ATP, and phosphocreatine (PCr).

Aim #2. To evaluate the effect of FPP on neuroinflammation, systemic inflammation, cognitive function, fatigue, and health-related quality of life.

Hypothesis: FPP will induce positive changes in neuroinflammation, systemic inflammation, cognitive function, fatigue, and health-related quality of life

6. Research Plan:

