Cerebral energy metabolism. Cerebral energy metabolism will be assessed by evaluation of change in creatine, phosphocreatine, α -ATP, β -ATP, and γ -ATP from in vivo 1H and 31P magnetic resonance spectroscopy (MRS) in the brain. We expect that these markers will increase with FPP, but not placebo.

Neuroinflammation. Neuroinflammation will be assessed in the brain using 1H-MRS markers of myo-inositol (MI) and choline (Cho), as well as diffusion-weighted magnetic resonance imaging (MRI) based quantification of extracellular freewater (FW).

- a) 1H-MRS: Elevated concentrations of myo-inositol and choline are indicative of increased neuroinflammation in the brain in both aging and medical conditions associated with elevated neuroinflammation (e.g., Alzheimer's Disease, HIV, etc.). We expect that MI and Cho will decrease with FPP, but not placebo.
- b) Freewater: Elevation in the concentration of extracellular freewater (e.g., edema) has been associated with increased neuroinflammation in advanced aging, head injury, dementia, and schizophrenia. We expect that extracellular freewater will decrease with FPP, but not placebo.

Cognitive Function. Cognitive function will be assessed using 1) a battery of standardized neurocognitive/neuropsychological tests (Table 1) assessing domains previously shown to decline in older adults, and 2) performance of a working memory task during functional magnetic resonance imaging (fMRI).

a) Neurocognitive Battery: The neurocognitive battery will assess change in cognitive function in domains including: learning, memory, working memory, attention,

executive function, language, and speed of processing. Table 1 shows the tests and affiliated domains tested.

b) fMRI Cognitive Assessment: The fMRI task will assess change in cognitive function by evaluating change in the functional response of the brain during performance of a difficult working memory task. This task will evaluate improvement in neural efficiency of processing with FPP versus placebo.

Table 1.Neurocognitive Assessment				
MoCA	Dementia Screen			
HVLT-R	Verbal Learning/Memory			
Stroop Test	Attention/Executive			
Trail Making A&B	Executive			
Boston Naming Test	Visual Recognition			
COWA	Verbal Fluency			
NIH Toolbox Subtests:				
Dimensional Card Sort	Executive Function			
Flanker Task	Attention/Executive			
Picture Sequence	Working Memory			
Auditory Verbal Learning	Episodic Memory			
Picture Vocabulary	Language			

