Weight & Waist Circumference							
Blood Pressure & Pulse							
Blood Chemistry Panel and Comprehensive Metabolic Panel							
Biomarkers of Inflammation (TNF-α, IL-6, IL1-beta, UCHL1, MPO)							
Biomarker of Inflammation (CRP)							
Biomarkers of Oxidative Stress							
Brain Magnetic Resonance Imaging/Magnetic Resonance Spectroscopy (cerebral energy metabolism, neuroinflammation, and cognitive brain function markers)							
Cognitive Testing							
Functional Assessment of Chronic Illness Therapy – Fatigue (FACIT Fatigue)							
Brief Fatigue Symptom Inventory							
RAND 36-Item Health Survey (SF-36)							
Dispense Study Product (FPP or Placebo)							
Phone Call Follow-up							

Table 3. Timeline for tests, evaluations, and protocols to be conducted and performed.

Notes: V1 (W0) = Baseline Visit; V2 (W8) = Visit 2, Week 8; V3 (W14) = Visit 3, Week 14; V4 (W22) = Visit 4, Week 22; Phone Call (W24) = Follow-up, Week 24.

Compliance checks and adverse event queries will occur by phone on a bi-weekly basis throughout the study.

7. Data Analysis:

Randomization. Osato Research Institute (Japan) will provide the blinded medication to the investigators. The two possible orderings (PA, AP, with P=Placebo, A=FPP dose) will be balanced throughout the study.

Study Design. (15 completers per ordering, 30 total). A cross-over (two-sample method) will be used, because it is more efficient and provides the value of approximately 3.6 participants as compared to one participant in a parallel study. The two-sample method is valid even with carryover and period effects, as it estimates the arithmetic mean of the period 1 and period 2 effects, a legitimate endpoint. Also, the method does not rely on any assumptions, as it leans on large sample theory, and except for anticipated outlier situations, the central limit theory assures rapid convergence of the *t*-statistic.

Power Analysis. Currently no data exists for in vivo change in brain markers of energy metabolism of neuroinflammation with FPP. Pilot data for systemic change in inflammation was used to obtain estimates of paired difference standard deviations for the power analysis.

Variable	Paired Diff SD (σ)	Detectable Difference (0.62σ)
MPO	19	12
IL6	8	5
TNF-α	15	9

Detectable differences with 80% power at p = 0.0167 (two-sided)

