Study Outcomes. The hypotheses comparing the treatments will be tested by the two-sample method for cross-over studies per Shuster (2007). Intent-to-treat analysis will be used, and analysis of variance (ANOVA) will be performed.

For the primary hypothesis, markers of cerebral energy metabolism will be assessed using phosphorus magnetic resonance spectroscopy markers of ATP/mitochondrial function in brain tissue (phosphocreatine, α -ATP, β -ATP, and γ -ATP). The 3 ATP peaks will be averaged to provide an overall marker of ATP in brain tissue. Phosphocreatine will be analyzed separately. Each pairwise contrast will be made stratifying for matched versus unmatched. Because two cerebral energy metabolism markers were selected, Bonferroni corrections will be used (p < 0.025). This strict requirement for significance ensures that the probability of falsely declaring any pair of treatments as significantly different when there is no difference in the target population is less than 5%. The secondary outcome variables will be analyzed in a similar manner, with any significant findings needing independent verification in a future study. If there are no unpaired data for a contrast, the method will be equivalent to that given in Shuster (2007).

Confidentiality of Participants and Data.

- a) Participant identifiers. The screening form, contact information form, consent form and the coding list (i.e., list of participant names and participant identification number) are the only study documents that will contain the participants' names and other personal data. All other study measures will be coded with a participant identification number that contains no identifying information that would connect to the participant. Screening form, contact information form, consent form, and coding list will be stored in a separate locked filing cabinet from all other study forms and materials.
- b) Data management & storage. The data will be managed via the REDCap data management software that produces SAS-ready datasets. The Clinical and Translational Science Institute (CTSI) Data Services Lab offers REDCap software as well as tutorials for using the software

so that researchers will be able to easily set up secure case report forms and a web-based database with on-site and off-site back-up. De-identified neuroimaging data will be uploaded to a secure file system for processing using neuroimaging software on the UF HiperGator Supercomputer.

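### Single-step Bonferroni on the two primary markers is valid, but Holm's step-down would keep the same 5% family error and be more likely to show both markers (optional improvement)

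*Combined protocol and SAP*

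**What the plan says.** Section 7 (Data Analysis), Study Outcomes, builds two primary markers from the phosphorus spectroscopy. For ATP, "The 3 ATP peaks will be averaged to provide an overall marker of ATP in brain tissue". For the other, "Phosphocreatine will be analyzed separately". It then sets the level: "Because two cerebral energy metabolism markers were selected, Bonferroni corrections will be used (p < 0.025". The stated purpose is a bound, in per cent: "the probability of falsely declaring any pair of treatments as significantly different when there is no difference in the target population is less than 5". No step-down, ordered or gatekeeping rule appears anywhere in the document.

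The Aim 1 hypothesis in section 5 (Specific Aims) is about all the markers together: "FPP will increase cerebral energy metabolism markers on alpha ATP, beta ATP, gamma ATP, and phosphocreatine (PCr". Section 6 (Research Plan), under Cerebral energy metabolism, repeats the expectation: "We expect that these markers will increase with FPP, but not placebo".

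On the design, section 7 gives "15 completers per ordering, 30 total", and on the test, "The hypotheses comparing the treatments will be tested by the two-sample method for cross-over studies". Nowhere does the document say whether Aim 1 is met by one significant marker or needs both.

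**The concern.** The plan predicts two effects but uses a rule under which success on one marker gives no help to the other. If one marker reaches p < 0.025 and the other has p between 0.025 and 0.05, the second is reported as not significant. Holm's procedure would declare it and still bound the family error at 5%, whatever the correlation between the markers.

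With 30 participants, and no sample-size calculation for these markers, that lost power could leave a two-marker hypothesis looking half supported.

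**Working it through.** **Inputs from the document.** Two primary markers; level 0.025 each; family target 5%; 30 completers, 15 per ordering; two-sample cross-over t method.

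**Assumed, because the document gives nothing.** Equal true effects *d* on both markers in paired-difference SD units (σ), varied from 0.30 to 0.62; correlation between the markers' paired differences from 0 to 0.6; two-sided tests. Section 7 itself says there are no data on change in these brain markers with FPP.

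**Step 1: reproduce the plan's figures.** The effect is the average of the two ordering means, so its variance is (σ²/15 + σ²/15)/4 = σ²/30, with 28 df. Solving the non-central t for 80% power at two-sided 0.0167 gives 0.623σ, against 0.62σ in the power table. For the level: 2 × 0.025 = 0.05. Both agree. The power table covers MPO, IL6 and TNF-α at 0.0167, not the two primary markers at 0.025. That is a separate matter.

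**Step 2: an effect for illustration.** At level 0.025, 80% power needs about 0.59σ. I use *d* = 0.588. Single-test power at this effect is *a* = 0.798 at level 0.025 and *b* = 0.875 at level 0.05.

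**Step 3: independent markers, by hand.**
- Both declared, Bonferroni: *a*² = 0.798² = 0.64.
- Both declared, Holm: *b*² − (*b* − *a*)² = 0.766 − 0.006 = 0.76. The subtracted term is the case in which both p-values lie between 0.025 and 0.05, so that Holm never starts.
- At least one declared, either rule: 1 − (1 − *a*)² = 1 − 0.041 = 0.96.
- Power per marker: *a* = 0.80 with Bonferroni; *a* + (*b* − *a*)*a* = 0.798 + 0.061 = 0.86 with Holm.

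**Step 4: correlated markers.** Simulation of 400,000 trials per setting, t with 28 df:

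| Effect on both | Correlation | Both, Bonferroni | Both, Holm | At least one, either rule |
|---|---|---|---|---|
| 0.588σ | 0 | 63.7% | 76.0% | 95.9% |
| 0.588σ | 0.3 | 66.0% | 77.1% | 93.3% |
| 0.588σ | 0.6 | 69.2% | 79.0% | 90.2% |
| 0.62σ | 0.3 | 72.7% | 82.5% | 95.6% |
| 0.50σ | 0.3 | 45.7% | 58.4% | 83.4% |
| 0.40σ | 0.3 | 24.0% | 34.6% | 64.3% |
| 0.30σ | 0.3 | 9.3% | 15.4% | 41.0% |

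Power per marker at 0.588σ rises from 80% to about 85–86%.

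**Step 5: error rates.**
- Both markers null: at least one false claim in 4.9% of trials at correlations 0 and 0.3, identical under the two rules and lower at higher correlation.
- One marker null, the other at 0.588σ, independent: the null marker is falsely declared in 2.5% with Bonferroni and in 0.025 + 0.025 × 0.798 = 4.5% with Holm. Simulation gives 4.2% at correlation 0.6. Both are within 5%.

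**The case against.** The strongest reply is that nothing here is wrong. The plan prespecifies two markers, a level for each and the guarantee it wants, and Bonferroni delivers that guarantee. The text itself describes the threshold as strict. It also gives 97.5% intervals that match the decisions, which matters in a pilot, where estimates count for more than whether a second p-value passes. All of this stands.

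Two further points also stand:
- The gain depends on a success rule that the document does not state. If one marker is enough, the gain is exactly zero. If both were formally required, no correction would be needed: testing each at 0.05 gives 77.8% against Holm's 77.1% (0.588σ, correlation 0.3). Holm suits the case between these, where either marker may be claimed alone and both are hoped for.
- The added power has a price when one marker is null (step 5 of the working).

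A reader might infer that Holm makes Aim 1 more likely to be confirmed outright. The documents do not support that, because they do not say that Aim 1 needs both markers. A reader might also infer from the single-test calculation at level 0.05 that the effect detectable with 80% power falls from 0.59σ to 0.53σ for the second marker. That holds only once the first marker has passed. With both effects at 0.53σ, Holm's actual power per marker is about 76–77%.

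What the reply does not remove is that Holm never gives fewer rejections than Bonferroni on any data set, has the same family bound and needs no assumption about correlation.

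**Conclusion.** The point holds as an optional efficiency gain, not as an error. Bonferroni as written is valid. Holm keeps the same 5% family bound, and the direction of the gain does not depend on any assumption.

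The size does. It rests on 30 completers, equal effects on both markers and assumed correlations. The gain in showing both markers is about 10 to 12 points at 0.588σ, and about 6 points at 0.30σ with correlation 0.3, where neither rule is likely to show both. The gain per marker at 0.588σ is about 5 to 6 points. The gain in showing at least one marker is nil.

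**What to change.** Before unblinding, replace the Bonferroni sentence in Study Outcomes by:

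> The two primary p-values are tested by Holm's procedure at a two-sided family level of 5%: the smaller against 0.025 and, if significant, the larger against 0.05. Effects are reported with 97.5% confidence intervals.

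Add a sentence saying whether Aim 1 is met by one marker or needs both, since the value of the change depends on it.

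The cost is analysis text only, with no extra participants, visits or measurements. There are two downsides. Holm's decisions do not map one-to-one onto the 97.5% intervals: a marker can be declared while its interval includes zero. And the false-claim rate for a null marker beside a responding one rises, within the promised 5%. The change is credible only if made before the p-values are seen.

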8. Possible Discomforts and Risks:

Risks Associated with consumption of Fermented Papaya Preparation. There are no known risks associated with the consumption of FPP. However, the primary ingredient in FPP is papaya, which is associated with some side effects. People with an allergy to papaya should not take FPP, because it may cause an allergic reaction. Large amounts of papaya can also lead to miscarriage in women and yellowing of palms and soles of feet.

Risks Associated with Placebo. There are no known risks associated with placebo.

Risks Associated with Blood Draw. There are risks of infection anytime the skin is punctured. Therefore, there is a minimal risk of infection due to the blood draw. To lower these risks, only certified phlebotomists using sterilized materials will perform the blood draw.

Risks Associated with Cognitive Function Tests. Participants may experience fatigue and feelings of frustration while completing the cognitive function tests. To minimize risk, participants will be able to skip any questions or tests that they do not wish to answer.

Risk associated with Brain Magnetic Resonance Imaging/Magnetic Resonance Spectroscopy. During the MRI/MRS procedure, participants will be able to talk with the MRI/MRS staff through a radio intercom speaker system, and, in the event of an emergency, they can tell them to stop the scan immediately. Participants will be asked frequently during the preparation and scanning period whether they are experiencing any discomfort, and corrections will be made as necessary._Participants may experience discomfort during the scanning process due to limited space inside the bore of the magnet. Subjects will be closely monitored and repeatedly checked by the investigators to ensure comfort. Participants may also become uncomfortable from lying still for an extended period of time, or if they do not like to be in close spaces (have "claustrophobia"). Padding with blankets can be used to prevent discomfort while lying in the magnet._The MRI/MRS scanner produces a loud "hammering" noise, which has been reported to produce temporary hearing loss in a very small number of people. Participants will be provided with earplugs to wear in the scanner, and also headphones to reduce this risk and possible discomfort.

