Suspected adverse reaction is any adverse event for which there is a reasonable possibility that the study product (i.e., fermented papaya preparation; FPP) **caused** the adverse event. The study physician and the Principal Investigator will evaluate the available information and decide whether there is a reasonable possibility that the study drug caused the adverse event and, therefore, that the event meets the definition of a suspected adverse reaction. Evidence to suggest a causal relationship between the study drug and adverse event includes: (1) Individual occurrence - a single occurrence of a serious adverse event that is uncommon and is known to be strongly associated with exposure to the study drug; (2) One or more occurrences - a single occurrences of a serious adverse event that is uncommon in the study population, but not commonly associated with drug exposure may also be informative; (3) Aggregate Analysis of Specific Events - events which occur more frequently in the active treatment group than in a concurrent control group; or, if a control group is not available, estimate whether the rate is greater than in a control population, general population, or populations similar to the drug population.

For events that require more than one occurrence to assess causality and events evaluated in the aggregate, the time frame starts when the investigator-sponsor determines that the events qualify for reporting. The investigator-sponsor must report in an IND safety report any suspected adverse reaction to study treatment (i.e., including active comparators) that is both serious and unexpected:

Unexpected suspected adverse reaction is an adverse event or adverse reaction that is not listed at the specificity or severity that has been previously observed; or, if an investigator brochure is not required or available and is not consistent with the risk information described in the general investigational plan.

Serious suspected adverse reaction is an adverse event or adverse reaction that results in any of the following outcomes:

a) A life-threatening adverse event or death;

b) Inpatient hospitalization or prolongation of existing hospitalization;

c) A persistent or significant incapacity or substantial disruption of the ability to conduct normal life functions;

d) A congenital anomaly/birth defect;

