e) Medical events that require medical or surgical intervention to prevent one of the outcomes listed in this definition.

A life-threatening suspected adverse reaction is an adverse event or adverse reaction that places the participant at immediate risk of death.

12.2 Adverse Events Collection Period:

Adverse events will be collected from the time the informed consent form is signed until the participant exits the study.

12.3 Review and Reporting of Adverse Events:

For the duration of the study, the participants will be directed to report any AEs to the study team. All AEs, regardless of assessment of causal relationship to study drug, must be reported to the investigator or investigators' designee. The study team will report AEs (i.e., any unfavorable and unintended sign (e.g., an abnormal laboratory finding deemed to be clinically significant), symptom, or disease) that are both unexpected and judged to be related to the study product to [name] within 24 hours following discovery by the study team. All other AEs should be reported to [name] within seven business days of discovery.

- A study physician must be responsible for all trial-related medical decisions and the review of AEs throughout the study. The physician will assess AEs and will assure that they are recorded in detail. Adverse events, whether in response to a query, observed by study team, or reported spontaneously, will be reported on the appropriate CRF and/or source document.
- Study progress and safety (e.g., cumulative table of adverse events and serious adverse events) will be reviewed monthly (and more frequently if needed) by the Principal Investigator.
- Progress reports, including adverse events will be provided to an Independent Monitoring Committee for bi-annual reviews. The Data and Safety Monitoring Committee (DSMB) for this study will consist of the following individuals: (1) [name]., Professor and Chief, Adult Division of Endocrinology, Diabetes & Metabolism in the Department of Medicine, a physician who has been involved in the conduct of clinical research for many years (2) [name]., Professor and Chief of the Division of Geriatric Medicine, a physician who has been involved in the conduct of clinical research for many years, and (3) [name]., an Assistant Professor who has conducted a number of clinical trials.

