An independent internal Data and Safety Monitoring Committee will conduct at least one interim review of safety data from the study. The need for subsequent reviews will be determined based upon the results of the first review.

• The time frame for submitting an IND safety report to FDA is no later than 15 calendar days after the investigator-sponsor determines that the suspected adverse reaction or other information qualifies for reporting.

• Any unexpected fatal or life-threatening suspected adverse reactions will be reported to the FDA no later than 7 calendar days after the initial receipt of the information.

[name] is responsible for the submission of AE reporting forms and any other supporting documentation to the IRB Administrative Office within 5 working days of discovery. If an event, incident, experience, or outcome is life-threatening or fatal, the IRB must be notified by phone within 24 hours.

If a suspected adverse reaction occurs that is both (1) serious, and (2) unexpected, the clinical product codes may be broken to the appropriate study team member if deemed necessary (i.e., the medical care of the participant would be altered by knowing product identity). Un-blinding can be accomplished by contacting [name]., a Biostatistician who will contact [name]. The study physician will direct the process in such a way as to not un-blind the study team members.

12.4 Review of the Study Overall:

Progress reports, including participant recruitment and retention/attrition, will be provided to the DSMB for bi-annual reviews.

- An annual report will be compiled and will include a list and summary of adverse events. In addition, the annual report will address:
 - 1) Whether adverse events are consistent with pre-study assumptions;
 - 2) Reason for dropouts from the study;
 - 3) Whether all participants met the study enrollment criteria;
 - 4) Whether continuation of the study is justified on the bases that additional data are needed to accomplish the stated aims of the study; and
 - 5) Conditions whereby the study might be terminated prematurely.
- The annual report will be signed by the chair of the Independent Monitoring Committee and will be forwarded to the IRB. The IRB and other applicable recipients will review progress of this study on an annual basis.

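### The code-break rule in section 12.3 lets medical need count only after the IND-reporting test is met, leaving a narrow set of events with no stated trigger

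*Combined protocol and SAP*

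**What the plan says.** Section 12.3 opens the code-break rule with a regulatory condition: "If a suspected adverse reaction occurs that is both (1) serious, and (2) unexpected, the clinical product codes may be broken". The sentence goes on to say that the code is "broken to the appropriate study team member if deemed necessary", and it explains necessity as the case where "the medical care of the participant would be altered by knowing product identity". What follows is a contact route through a biostatistician and an instruction that the study physician manage the process so that the study team stays blinded. Neither adds a further trigger.

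Section 12.1 uses the same elements to decide what goes to FDA. Its rule begins "The investigator-sponsor must report in an IND safety report any suspected adverse reaction to study treatment (i.e., including active comparators) that is both", and the two properties it then names are seriousness and unexpectedness. On whether an event counts as suspected, meaning possibly caused by the product, it says: "The study physician and the Principal Investigator will evaluate the available information and decide whether there is a reasonable possibility". An event is unexpected if it is not listed at the specificity or severity already observed or, where no investigator brochure is required or available, if it is "not consistent with the risk information described in the general investigational plan".

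Section 12.3 also states: "A study physician must be responsible for all trial-related medical decisions and the review of AEs throughout the study". That provision does not mention the codes.

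**The concern.** A code break and an expedited safety report answer different questions. The report tells the regulator about a possible new harm, so it is right to ask whether the event was suspected, serious and unexpected. A code break tells a physician what one participant has been taking, and the relevant question is whether that knowledge changes care. Section 12.3 asks the second question only of events that have passed the first test.

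Two mismatches follow. A risk the protocol already names is the kind most likely to be judged expected, and so to fall outside the rule. And an event must be attributed to FPP before the code may be broken, although knowing whether the participant was on FPP would inform that attribution. What is at stake is a participant's care in an uncommon situation. Alpha, power and the treatment estimate are not in question.

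**Working it through.** There is no plan figure to reproduce. The check is a reading of section 12.3 against sections 8 and 12.1 and Table 2, followed by arithmetic on what the remedy would cost.

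**The rule as written**
- Section 12.3: code may be broken if (suspected AND serious AND unexpected) AND (care would be altered).
- IND report, section 12.1: suspected AND serious AND unexpected.
- The first bracket of the code-break rule is therefore the IND test. The events with no stated trigger are those where care would be altered but the IND test is not met.
- No other section supplies a trigger. Section 7 says only that the product arrives blinded.

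**Which events fall in the gap**
1. *Serious, suspected, of a listed kind.* Section 8 names allergic reaction as a risk for people allergic to papaya. Table 2 excludes known allergy to papaya, related foods and latex, but a first reaction in someone with no known allergy remains possible. If it is judged expected, the rule does not reach it. Acute treatment would not wait for the code, but later advice on avoiding papaya could depend on it (a clinical inference, not in the documents). A reaction more severe or more specific than listed would count as unexpected and would be covered.
2. *Serious, not yet attributed or judged unrelated.* Until the study physician and the Principal Investigator decide that FPP may be the cause, the event is not a suspected reaction and the rule does not apply.
3. *Suspected, unexpected, not serious.* This is also outside the rule, but it is the weakest case. Section 12.1 foresees stopping the product for moderate events, and stopping needs no code.

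**Cost of one extra unblinding**
- Inputs: 30 participants, 15 per ordering (section 7); self-report questionnaires at each of the four assessment visits, V1 to V4 (section 6).
- With only two orderings, one code reveals both periods for that participant: 1/30 = 3.3% of the trial, 1/15 = 6.7% of one ordering.
- Self-report participant-visits: 30 × 4 = 120.
- Broken between V1 and V2, leaving V2, V3 and V4: 3/120 = 2.5%.
- Broken in washout, leaving V3 and V4: 2/120 = 1.7%.
- Broken between V3 and V4, leaving V4: 1/120 = 0.8%.
- The visit marks in Table 3 did not survive in the supplied text. If the cognitive battery is also given at all four visits (an assumption), the same counts apply to it.
- The primary outcome is spectroscopy (section 7), not self-report or a staff-administered test.

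**The case against.** The strongest reply is that the entry condition seldom binds. Section 8 says FPP has no known risks and ties what it lists to papaya, to large amounts or to people with papaya allergy, so nearly any event at 9 g a day could be called unexpected. Suspicion requires only a reasonable chance of causation, and where product identity would change care FPP is usually already a candidate cause. Seriousness reaches substantial disruption of normal life and events needing intervention to prevent a serious outcome. Medical need is inside the rule, the verb is *may*, and the study physician holds responsibility for medical decisions. Restricting code breaks for non-serious events in a small blinded cross-over is a defensible choice.

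Most of this stands and limits the point. It does not close the two serious cases above, which still have no written trigger.

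A reader might infer something stronger from the text, in three ways the documents do not support:
- *That unblinding for medical need is prohibited or ignored.* Nothing forbids it, and need is the stated meaning of necessity.
- *That the study has no emergency route at all.* A contact route is written, and contact and consent pages, where further instructions would naturally sit, were removed from the supplied text.
- *That the yellowing of palms and soles mentioned in section 8 shows the gap.* The text ties it to large amounts of papaya, and the metabolic panel in section 6 (bilirubin, ALT, AST) would address much of the question without the code.

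**Conclusion.** The point holds in a limited form, as a low-confidence suggestion worth considering. The one code-break rule in the supplied text is keyed to a reporting criterion and leaves some serious events without a stated trigger when care may depend on product identity. The size of the gap cannot be quantified: the documents give no rate of such events, and section 4 reports no adverse events in the cited human studies. The percentages above measure the cost of the remedy, not the frequency of the problem.

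The conclusion assumes that the removed pages contain no separate emergency instruction, that a serious allergic reaction could be judged expected on the section 8 text (any investigator brochure is not among the documents), and that product identity could matter to later care in the cases described. A reader might go further and infer that participants are likely to be harmed; nothing in the documents supports that.

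**What to change.** Reword the entry condition in section 12.3 so that the study physician may have an individual participant's code broken whenever knowing product identity would alter that participant's medical care, regardless of seriousness, expectedness or attribution. Keep the suspected, serious and unexpected test for IND reporting only. Leave the IRB reporting, the contact route and the shielding of the remaining team as they are. Add that a team member who learns the code does not run that participant's later cognitive or self-report assessments.

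The drafting cost is small. The operational cost is an occasional extra unblinding that lasts for the rest of that participant's cross-over and, if the participant also learns the product, may colour later fatigue and SF-36 answers. The need test stays in place, so the change does not allow unblinding at will.
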